### 3-month Post-Procedure Phone Call:

All patients at 3-month post-procedure visit will receive:

- a. AUA-SI, PPBC, OABq-SF, PPBC (per standard clinical practice)
- b. Post-Botox 3-Month Post Procedure Survey

**Symptoms assessment:** Participants will be asked, by phone, standardized, validated questionnaires documenting urinary symptoms and quality of life for comparison. Instruments will include the American Urologic Association Symptom Index (AUA-SI), Overactive Bladder Questionnaire short-form (OABq-SF), Patient Perception of Bladder Control questionnaire (PPBC) and the Patient's Global Impression of Improvement (PGII).

**Urinary tract infection:** Patients will be asked about presence and frequency of UTI including treatment and duration of treatment.

**Treatment success:** Patients will be assessed at post-procedure phone call at 3 months. Efficacy of injection will be assessed via inter-injection times for patients receiving multiple injections and will be followed for the duration of the study period.

### 2nd Injection:

Patients will have been consented at the beginning of the study to include both 1st and second injections and therefore do not need to be re-consented. The exact protocol is followed as stated above, however, patients will receive the treatment from the arm NOT received after the first injection. For example, patients who received extended 3 day course of antibiotics after the first injection, will receive only peri-procedural antibiotics after the 2nd injection.

The timing of the second injection will be determined by the clinician and patient based on symptoms and will not be standardized.

### Randomization

Every patient will receive Extended Dose Antibiotics (EDA) and Peri-Procedural Antibiotics (PPA). The patients will be randomized to receive EDA or PPA at the first visit or second visit. A block randomization with block sizes of 2 and 4 will be used. The exact numbers of size 2- and size 4- blocks will be randomly chosen so that approximately 70% of blocks will be allocated to 'block of size 4'.

### Statistical analysis plan

The primary endpoint is the presence (Yes/No) of urinary tract infection 3 weeks post procedure. We will estimate the probability of urinary tract infection for both treatment groups. Baseline patient-characteristics data will be collected and tabulated. The trial design (crossover) will guarantee that the baseline covariates will be distributed similarly for both treatment groups. Carryover effect is minimized since the time between the first and second injections is sufficiently long for any residual treatment effect from the first period to wear off. For each treatment, the probability of UTI will be estimated and presented with 95% Wilson confidence intervals. We aim to establish non-inferiority of EDA to PPA with the non-inferiority margin of 10 percentage points. We will estimate the proportion of patients who will have infection with EDA but not with PPA.

Sample size and power were computed using the method described in Chow et al . To compute the sample size, we need to specify, in addition to the usual parameters (type I error rate of 5%, type II error rate of 10%, non-inferiority margin of 0.10, and difference under the alternative of 0), the variance of difference, which takes value of 1 if only EDA is successful, -1 if only PPA is successful, and 0 if EDA and PPA yield the same outcome. This variance, in turn, depends on the true probability of infection with EDA and PPA and also concordance of the result (success/failure) within a given patient. Under a pessimistic scenario where P[infection] is 25% and 35%, and the concordance is weak (Knowing the result of other treatment only changes the probability by 5 percentage points for the patient), the variance is 0.40, and the corresponding sample size is 68. Even if the true P[infection] is 35% and 45%, we will maintain the excellent power as shown below in the Table.

Power with n=68

P[infection] with EDA	0.25	0.25	0.35	0.35
P[infection] with PPA	0.35	0.35	0.45	0.45
Concordance	+0.05	+0.10	+0.05	+0.10
Power	90%	92%	83%	86%

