#### **Established patients:**

Established patients continuing injection will be screened and consented on the day of presentation for injection. PVR within 8 weeks must be documented in chart. If no PVR documented within 8 weeks, must repeat PVR prior to injection with either a bladder scanner or catheterized value. UA obtained per existing clinic policy. Eligibility determined by provider based on UA and PVR.

Demographic information including comorbidities will be abstracted from patients' electronic medical records, and a focused history and physical will be performed on day of injection.

**Injection protocol:** All patients will undergo injection per a standardized protocol of 1ml injection per site at a concentration of 10 units/ml. For patients undergoing injection in the clinic setting, an intravesical instillation of diluted local anesthetic will be used prior to injection, if no allergy to anesthetic is reported. For those performed in the operating room, anesthesia will be administered per the discretion of anesthesiology team. The number of units injected will be documented and accounted for during analysis by stratifying patients according to the amount of BTX-A injected.

**Antibiotic protocol:** On the day of injection patients will be randomized to either the experimental or control arm according to a computer generated randomization scheme (see explanation of randomization below). Patients randomized to the experimental arm will receive a single dose of trimethoprim/sulfamethoxazole (800/160mg) peri-procedurally. Patients randomized to the control arm will receive one dose of trimethoprim/sulfamethoxazole peri-procedurally and additionally be prescribed trimethoprim/sulfamethoxazole twice daily for three days. Patients who are allergic will receive amoxicillin/clavulanic acid (875/125mg) twice daily for three days. If allergic to both of the above antibiotics, patients will receive 100mg nitrofurantoin BID for three days. Our budget reflects published data regarding our local antibiogram and population estimates for antibiotic allergies.

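### The stated analysis gives separate Wilson intervals and one discordant proportion, so nothing in it compares the paired treatment difference with the 10-point margin, and the direction of non-inferiority is contradicted elsewhere

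*Combined protocol and SAP*

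**What the plan says.** The Statistical analysis plan section is the whole analysis plan. It opens with the endpoint: "The primary endpoint is the presence (Yes/No) of urinary tract infection 3 weeks post procedure". The inferential output is then given as: "For each treatment, the probability of UTI will be estimated and presented with 95% Wilson confidence intervals". The aim follows: "We aim to establish non-inferiority of EDA to PPA with the non-inferiority margin of 10 percentage points". One quantity that uses the pairing is also planned: "We will estimate the proportion of patients who will have infection with EDA but not with PPA". No interval or test is attached to it.

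The sample-size paragraph works with a within-patient variable, "which takes value of 1 if only EDA is successful, -1 if only PPA is successful", and zero when the two outcomes agree. Its inputs are "type I error rate of 5%, type II error rate of 10%, non-inferiority margin of 0.10, and difference under the alternative of 0", and it reports that "the variance is 0.40, and the corresponding sample size is 68". It does not say whether the 5% is one- or two-sided. The textbook method is cited for sample size and power, not for the analysis.

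The Antibiotic protocol paragraph (under Established patients) assigns the labels: "Patients randomized to the experimental arm will receive a single dose of trimethoprim/sulfamethoxazole (800/160mg) peri-procedurally". The control arm there adds the three-day course.

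**The concern.** Every patient receives both treatments, so the two outcomes come in pairs. The variability of the treatment difference depends on how many patients have discordant outcomes. The sample-size paragraph recognises this, but the analysis text does not carry it through. A Wilson interval for each treatment says nothing about discordance. The EDA-only proportion is one of the two cells whose difference is the treatment effect, so by itself it is not a risk difference.

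The plan therefore has an aim and a margin, but no stated interval, test or rule that joins them. The level and the rule would have to be supplied later. The direction matters as well, because a non-inferiority rule is one-directional. The analysis section asks whether EDA is no worse than PPA. The arm labels in the Antibiotic protocol suggest the reverse question.

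**Working it through.** **Inputs.** From the Statistical analysis plan: n = 68, margin 0.10, type I error 5%, 90% power, true difference 0, variance of the within-patient difference 0.40. The infection counts below are illustrative assumptions. Let b be the number infected on EDA only and c the number infected on PPA only; the difference EDA minus PPA is (b − c)/n.

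**1. What the plan's own figure implies about sidedness.** The usual paired formula is n = variance × (z_alpha + z_power)² / margin².
- One-sided 5%: 0.40 × (1.645 + 1.282)² / 0.10² gives 343.
- Two-sided 5%: 0.40 × (1.960 + 1.282)² / 0.10² gives 421.

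Neither is 68. Of the variants tried, one returns 68: entering 0.40 as a standard deviation in a per-sequence crossover formula at one-sided 5%, 0.40² × (1.645 + 1.282)² / (2 × 0.10²) = 68.5. The same route at two-sided 5% gives 84.1. The arithmetic therefore points to one-sided 5%, but only by inference.

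**2. The same Wilson intervals, different paired results.** With 17/68 infected on each treatment, each 95% Wilson interval is 16.2% to 36.4%, whatever the pairing. The observed difference is 0 and the Wald standard error is √(b + c)/68.

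| Discordant (b, c) | Wald SE | Wald 90% upper limit | Score (Tango) 90% upper limit | Margin |
|---|---|---|---|---|
| 3, 3 | √6/68 = 0.0360 | 5.9 points | 6.9 points | met |
| 13, 13 | √26/68 = 0.0750 | 12.3 points | 12.5 points | not met |

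The first row shows what is logically possible; it is not a likely result. It means 14 patients infected on both treatments, so P(infected on PPA) is 14/17 = 82% among those infected on EDA and 3/51 = 6% among the rest. The plan assumes shifts of only 5 to 10 points. Under independence at 25%, the expected discordant count is 68 × 2 × 0.25 × 0.75 = 25.5, close to the second row.

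**3. A data set near the plan's variance.** Take b = 12, c = 15 (27 of 68 discordant; 27/68 = 0.40). The difference is −3/68 = −4.4 points. The score statistic at d = 0.10 is (b − c − nd)/√(n[2q + d(1 − d)]), where q is the PPA-only probability estimated under that difference:
- q = (√(B² − 4AC) − B)/(2A), with A = 2n = 136, B = −27 + 139 × 0.10 = −13.1 and C = −15 × 0.10 × 0.90 = −1.35. This gives q = 0.159.
- The statistic is −9.8/5.265 = −1.86, one-sided p = 0.031.

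The upper limit is 8.3 points at two-sided 90% (met) and 10.8 at 95% (not met). The Wald limits are 8.1 and 10.5.

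**4. Direction, same data.** The 90% score interval for EDA minus PPA is −17.0 to 8.3 points. EDA non-inferior to PPA is met (8.3 < 10). PPA non-inferior to EDA is not met, because the upper limit of PPA minus EDA is 17.0.

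**5. How often the level matters.** Exact enumeration of the trinomial outcome, n = 68, score rule, direction as in the analysis section:

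| True EDA − PPA | P(EDA only), P(PPA only) | Met, one-sided 5% | Met, one-sided 2.5% | Changed by level |
|---|---|---|---|---|
| 0 | 0.20, 0.20 | 37.3% | 24.9% | 12.4% |
| −10 points | 0.155, 0.255 | 83.3% | 72.8% | 10.5% |

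Variance is 0.40 in both rows (0.41 − 0.10² = 0.40 in the second). Wald and score rules at 90% disagree in 0.04% of trials at a difference of 0.

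**6. Precision.** SE = √(0.40/68) = 0.0767, so the 90% half-width is 1.645 × 0.0767 = 12.6 points. The observed difference would have to be about 10 − 12.6 = −2.6 points or lower to meet the margin.

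**The case against.** The strongest reply is that the plan is short rather than wrong. It states an aim, a direction, a margin, an error rate and a within-patient variable, and a competent statistician would naturally set a bound on the paired difference against 10 points. That is fair as far as it goes. A reader might infer that non-inferiority will never be tested, or that the trial cannot answer its question; the documents do not show that. They show only that no stated analysis makes the comparison. The reply does not remove the defect, because the plan does name its intervals, and they are the wrong kind for paired data and this margin.

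A reader might also infer that the two error levels are equally open, or that the level would be picked after the data are seen. The first ignores the arithmetic pointing to one-sided 5%. The second is a risk that the silence leaves, not something the documents indicate. Taken alone, the missing sidedness is missing detail.

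Two cautions on size also stand. The effect of the level depends on the true difference, so the 12.4% should not be quoted without the 10.5%. The example with 3 discordant patients each way is far from the weak concordance the plan assumes, so it should not be read as the variation to expect in practice.

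**Conclusion.** The point holds: the stated primary analysis ignores the pairing and contains no comparison of the treatment difference with the 10-point margin. Identical Wilson intervals can accompany a paired result that meets the margin or one that misses it. This is a wrong choice of stated output, not only brevity, and it must be corrected before the analysis.

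The conflict over direction is real and can reverse a conclusion, as the 12-and-15 example shows. The documents do not settle which direction is intended. The unstated level has a moderate effect, about 10% to 12% of trials, assuming variance 0.40, 68 complete pairs and a true difference between −10 points and 0. The choice between score and Wald intervals is minor.

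The failure of the stated inputs to give 68, and the low power that follows, is a separate issue and adds no weight here.

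**What to change.** Amend the Statistical analysis plan as follows.

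- **Primary analysis:** the paired risk difference in UTI at 3 weeks, with a valid paired interval (score or Wald, named in advance).
- **Direction and sign:** first reconcile the Antibiotic protocol labels with the direction in the analysis section. Then state the sign convention. The sample-size variable is +1 when only EDA succeeds, so, taking success as no infection, it runs opposite to an infection difference of EDA minus PPA.
- **Rule:** conclude non-inferiority only if the relevant limit, in the agreed direction, is within 10 points.
- **Level:** state whether the 5% is one-sided. If it is, the matching interval is two-sided 90%, not the 95% used for the Wilson intervals.
- **Description:** keep the Wilson intervals and the EDA-only proportion as descriptive output, and report the PPA-only proportion beside it.

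The cost is a few sentences and a little more analysis, with no new data. The drawback is that the rule makes the limited precision plain: at variance 0.40 the 90% half-width of about 12.6 points exceeds the margin. The rule does not cure that, so it should be read alongside the sample-size issue.

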**Protocol/SAP**

**October 6, 2018**

# Research Protocol

## Initial Visit

**Study population.** Enrollment is planned to achieve a total of 68 patients, with each subject undergoing two injections. All patients will receive 2 injections over the study time period as part of this cross-over study. Participants must be adult patients (age 18 or older) with medication-refractory non-neurogenic OAB subject to the following inclusion and exclusion criteria (Table 1). Patients who elect to proceed with intravesical BTX-A injection as third line therapy, and are deemed appropriate for treatment by the clinician, will be considered for eligibility. Patients presenting for injection will be screened and consented prior to the first injection, and this consent will apply for the duration of the study (over two injections).

**Demographic and clinical data:** Participants will complete a standardized questionnaire assessing demographics and pertinent medical history including surgical history, current and past OAB therapy, history of urinary tract infections (UTIs) and urinary retention, and self-reported diagnoses of comorbid medical conditions. We will supplement this information with abstracted data from electronic medical records on past medical and surgical history, urinalysis, urine culture data, and post-void residual.

**Note:** Recurrent UTI will be defined as three or greater culture documented UTIs within a 12 month period.

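### The sample size of 68 and the 83–92% power table do not follow from the plan's own inputs, which require 343 patients and give about 37% power at 68

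*Combined protocol and SAP*

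**What the plan says.** All the sample-size inputs are printed in the Statistical analysis plan. The aim is given as "We aim to establish non-inferiority of EDA to PPA with the non-inferiority margin of 10 percentage points". The parameters are a "type I error rate of 5%, type II error rate of 10" per cent, and a "non-inferiority margin of 0.10, and difference under the alternative of 0". Whether the 5% is one-sided or two-sided is not stated.

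The quantity analysed is the within-patient difference, coded +1, −1 or 0. For infection rates of 25% (EDA) and 35% (PPA) with weak concordance, the plan says "the variance is 0.40, and the corresponding sample size is 68". The table then gives power at n=68 of 90%, 92%, 83% and 86%, introduced by "Even if the true P[infection] is 35% and 45%, we will maintain the excellent power".

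The Initial Visit section fixes what 68 means: "Enrollment is planned to achieve a total of 68 patients, with each subject undergoing two injections". It is the total number of patients, and so the number of pairs. Under Randomization, "The patients will be randomized to receive EDA or PPA at the first visit or second visit", so the 68 are divided between two sequences.

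**The concern.** A variance of 0.40 is large against a margin of 0.10. With 68 pairs the standard error of the difference is √(0.40/68) = 0.077, so the margin is only 1.3 standard errors from a true difference of zero. A one-sided 5% test already uses 1.645 of those, so 90% power is not possible.

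The text and table also disagree. The text assumes no difference, but in every table column EDA is 10 points better. The direction is unsettled too. The Statistical analysis plan tests EDA against PPA, while the Antibiotic protocol makes the single-dose regimen experimental ("Patients randomized to the experimental arm will receive a single dose of trimethoprim/sulfamethoxazole").

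At stake is what the primary analysis can show. A trial that readers believe has 90% power, but in fact has about 37% at its planning rates, will probably miss its margin even if the two regimens are equivalent. That failure could then be misread as evidence that they differ.

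**Working it through.** **Inputs from the documents.** N = 68 total; margin 0.10; true difference 0; type I error 5%; power 90%; variance V = 0.40. One-sided 5% is my assumption, and it is the reading more favourable to the plan.

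**Step 1: the variance.** The two binomial variances are 0.25 × 0.75 = 0.1875 and 0.35 × 0.65 = 0.2275, which sum to 0.415. Suppose +0.05 is the difference in PPA infection risk between patients with and without EDA infection. The covariance is then 0.05 × 0.1875 = 0.0094, and V = 0.415 − 2 × 0.0094 = 0.396. The 0.40 is therefore reasonable, and the error comes after it.

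**Step 2: from the variance to N.** With d the distance from the true difference to the margin:

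- N = (z₁₋α + z₀.₉₀)² × V / d²
- power = Φ(d / √(V/N) − z₁₋α)

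At d = 0.10:

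- One-sided 5%: N = (1.645 + 1.282)² × 0.40 / 0.01 = 342.6, so 343. Power at 68 = Φ(1.304 − 1.645) = 36.7%.
- Two-sided 5%: N = 420.3, so 421. Power at 68 = Φ(1.304 − 1.960) = 25.6%.
- If 68 were per sequence (136 in total), one-sided: Φ(1.844 − 1.645) = 57.9%.

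Simulating a paired score test with equal rates of 30% and correlation 0.05 gave 37.3% power at N = 68 and 90.1% at N = 343. For 68 to be right at difference 0, one-sided, V would have to be 68 × 0.01 / 8.564 = 0.079.

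**Step 3: the table's 10-point advantage.** If EDA is truly 10 points better and is tested as non-inferior to PPA, d = 0.20. One-sided: N = 8.564 × 0.40 / 0.04 = 85.6, so 86; power at 68 = Φ(2.608 − 1.645) = 83.2%. Two-sided: 106 patients and 74.1%.

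**Step 4: all four columns, one-sided 5%.** The plan prints a variance only for the first column. The other three come from the concordance reading in Step 1, rounded to two decimals.

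| EDA/PPA, concordance | V | Stated power | Power at 68, difference 0 | N for 90% | Power at 68, EDA 10 points better | N for 90% |
|---|---|---|---|---|---|---|
| 25/35%, +0.05 | 0.40 | 90% | 37% | 343 | 83% | 86 |
| 25/35%, +0.10 | 0.38 | 92% | 38% | 326 | 85% | 82 |
| 35/45%, +0.05 | 0.45 | 83% | 34% | 386 | 79% | 97 |
| 35/45%, +0.10 | 0.43 | 86% | 35% | 369 | 81% | 93 |

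Across six readings of concordance, power at 68 with difference 0 ranged from 33% to 48%.

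**Step 5: the opposite direction.** If PPA is tested against EDA, the table's true rates put PPA exactly 10 points worse, which is on the margin. Power there is only the type I error.

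**Step 6: precision.** At N = 68 and V = 0.40 the half-width is 1.645 × 0.0767 = 12.6 points for a 90% interval and 1.960 × 0.0767 = 15.0 points for a 95% interval. EDA would have to be observed at least 2.6 or 5.0 points better to clear a 10-point margin.

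**A possible origin (inference only).** Entering 0.40 as a standard deviation and taking a per-sequence number as the total gives 8.564 × 0.16 / (2 × 0.01) = 68.5. With the four values of V used as standard deviations and 136 patients, power is 89.8%, 92.3%, 82.8% and 85.7%, which round to the table. Unrounded variances miss two columns by a point. Correcting one slip alone is not enough: 136 patients with variance 0.40 give 58%, and 68 with standard deviation 0.40 give 66%. The finding does not depend on this explanation.

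**The case against.** The best defence is that the table, not the sentence about a zero difference, shows what was intended. Taken literally, its columns have EDA 10 points better, and the first-column shortfall is then 83% against 90%, not 37% against 90%. That is a fair reading of the columns, but it contradicts an explicit input, still does not reproduce the table, and works only if EDA is the regimen tested against PPA.

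Second, the plan calls 25/35% pessimistic, and lower infection rates would raise power. This is true. With equal rates, concordance +0.05 and V = 2p(1−p) × 0.95, one-sided power at 68 by formula (simulated score test in brackets) is 51% (49%) at a rate of 15%, 64% (58%) at 10% and 86% (77%) at 5%. The formula reaches 90% only at about 4.4%. The documents give no such rates, and the plan claims high power at the pessimistic ones.

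Third, only the 0.40 is printed, so the other three columns rest on a reading of concordance. That stands as a limit on those columns. It does not affect 343 or 37%, and no reading tried reaches the stated power at difference 0.

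Fourth, the plan gives Wilson intervals per treatment and names no test or interval for the paired difference. The precision figures therefore assume the usual rule, that the confidence limit for the difference must lie inside the margin.

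**Conclusion.** The concern holds. On the inputs as printed, 90% power needs 343 patients rather than 68, about a fivefold gap, and 68 patients give 37%. This assumes a one-sided 5% test, the normal approximation and complete data from both injections for all 68. A two-sided test makes it worse. The milder reading, with EDA truly 10 points better, narrows the gap but still gives 83% and 86 patients. At the planning rates and the usual interval rule, an observed difference of exactly zero would fail the margin, so failure would say little about whether the regimens differ.

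**What to change.** Revise the sample-size paragraph and table in the Statistical analysis plan:

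1. State whether the 5% is one-sided or two-sided, and name the test or interval for the paired difference.
2. Reconcile the direction of the hypothesis with the arm labels in the Antibiotic protocol.
3. Use the same true difference in text and table. Either keep 0 and show equal rates in each column, or adopt the 10-point difference. The second option makes sense only if EDA is tested against PPA.
4. Give the variance used for each column and define concordance.
5. Recompute. With difference 0, variance 0.40 and a one-sided 5% test, the corrected statement is about 37% power at 68 and 343 patients for 90%.
6. Delete the claim of excellent power.

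If enrolment stays at 68, report the paired difference with its interval and say in advance that missing the margin is not evidence of inferiority.

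The cost is protocol and SAP wording plus a corrected table. The stated power becomes much less favourable, but the restatement itself requires no additional patients.

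### The power calculation assumes no true difference, but every column of the power table has rates 10 points apart (the size of the margin), and the printed row is not the power of 68 patients at those rates

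*Combined protocol and SAP*

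**What the plan says.** The Statistical analysis plan lists its inputs as "type I error rate of 5%, type II error rate of 10%, non-inferiority margin of 0.10, and difference under the alternative of 0". The within-patient difference is coded as a variable "which takes value of 1 if only EDA is successful, -1 if only PPA is successful", and 0 when both treatments give the same outcome. Its variance is said to depend on the two true infection rates and on "concordance of the result (success/failure) within a given patient". The rates then come in: "Under a pessimistic scenario where P[infection] is 25% and 35%, and the concordance is weak", for which "the variance is 0.40, and the corresponding sample size is 68".

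The table headed for n=68 has four columns. Two have EDA 0.25 and PPA 0.35, and two have EDA 0.35 and PPA 0.45, with concordance +0.05 or +0.10 in each pair. The printed power is 90%, 92%, 83% and 86%. Of the second pair of rates the plan says: "Even if the true P[infection] is 35% and 45%, we will maintain the excellent power as shown below in the Table".

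On direction, the analysis plan says: "We aim to establish non-inferiority of EDA to PPA with the non-inferiority margin of 10 percentage points". The Antibiotic protocol attaches the experimental label to the other treatment: "Patients randomized to the experimental arm will receive a single dose of trimethoprim/sulfamethoxazole". The section on study population makes 68 the total number of patients, each receiving both treatments.

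**The concern.** On the plan's own coding, the mean difference at any tabulated pair of rates is P(infection, PPA) − P(infection, EDA) = +0.10, not 0. A zero difference and these rates therefore cannot describe the same truth. The gap also equals the margin, so the result depends heavily on which arm is tested:

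- **EDA tested against PPA:** the tabulated truth is favourable, lying 0.20 from the null boundary.
- **PPA tested against EDA:** the tabulated truth lies on the null boundary, where a valid test succeeds only at the type I error rate.

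The table is the only support the plan gives for 68 patients, and its text tells readers that power stays high if these rates are the true ones.

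**Working it through.** **Inputs (Statistical analysis plan).** Margin 0.10; type I error 5%, sidedness not stated, taken as one-sided with 2.5% shown for comparison; n = 68 patients in total; variance V = 0.40 for column 1; rates and concordance values as tabulated.

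**Formula.** Paired normal approximation: power = Φ(D / √(V/n) − z), where D is the distance from the true difference to the null boundary, and z = 1.645 (one-sided 5%) or 1.960 (one-sided 2.5%).

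**1. The plan's own figures.** With the inputs as written (difference 0, so D = 0.10), √(0.40/68) = 0.0767 and power = Φ(1.304 − 1.645) ≈ 37%, not 90%. The printed row comes back only if 68 is taken as the number per sequence (136 patients) and the value 0.40 is entered as a standard deviation: n = (1.645 + 1.282)² × 0.40² / (2 × 0.10²) = 68.5. With the variances of reading D below used in this way, power is 90.3/92.6/82.5/85.8%. This shows how the row may have arisen. That variance and per-sequence error is a separate matter and is not counted in the size of this point.

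**2. Column 1 at its labelled rates.** No reading of concordance is needed here.

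- EDA tested: D = 0.10 + 0.10 = 0.20. Power = Φ(0.20/0.0767 − 1.645) = Φ(0.963) = 83.2%. At one-sided 2.5% it is 74.1%.
- PPA tested: D = 0.10 − 0.10 = 0. Power = Φ(−1.645) = 5.0%. At one-sided 2.5% it is 2.5%.
- Rounding of V (0.395 to 0.405) moves the 83.2% only between 83.6% and 82.8%.
- A simulation of 400,000 trials with P(only EDA succeeds) = 0.255 and P(only PPA succeeds) = 0.155, which gives mean 0.10 and V = 0.41 − 0.01 = 0.40, returned 83.4% and 5.2%.
- For 90% at D = 0.20, V would have to be 68 × (0.20/2.926)² = 0.318. With V = 0.40, n would have to be 2.926² × 0.40/0.04 = 85.6.

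**3. All columns, EDA tested, one-sided 5%.** Concordance has no formula in the plan, so seven readings were tried. In each, V = pE + pP − 2·P(both infected) − 0.10², where pE and pP are the infection rates and c is the concordance value.

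| Reading of concordance c | V, column 1 | Power (%), columns 1 to 4 |
|---|---|---|
| A: P(EDA inf given PPA inf) = pE + c | 0.380 | 84.9 / 87.8 / 80.8 / 84.5 |
| B: P(PPA inf given EDA inf) = pP + c | 0.390 | 84.0 / 86.1 / 80.0 / 82.8 |
| C: P(EDA inf given PPA inf) − P(EDA inf given PPA not) = c | 0.392 | 83.9 / 85.7 / 79.2 / 81.2 |
| D: as C, arms swapped | 0.396 | 83.5 / 85.1 / 79.0 / 80.8 |
| E: phi correlation = c | 0.394 | 83.7 / 85.4 / 79.1 / 81.0 |
| F: P(EDA success given PPA success) = (1 − pE) + c | 0.350 | 87.3 / 92.6 / 81.6 / 86.1 |
| G: P(PPA success given EDA success) = (1 − pP) + c | 0.340 | 88.2 / 94.0 / 82.4 / 87.8 |
| **Printed** | **0.40** | **90 / 92 / 83 / 86** |

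Reading D is closest to the stated variance and falls 4 to 7 points below print. At one-sided 2.5% the readings run from 69% to 89%.

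**4. All columns, PPA tested.** D = 0 throughout, so power is 5% in every column under every reading (5.2 to 5.5% in simulation).

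**5. Effect of relabelling alone.** Replacing the rates with equal ones (30/30 and 40/40), deriving the variance from them and keeping the difference at 0, moves power by −1.7 to +0.5 points over the seven readings.

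**The case against.** The best defence is that the rates serve only to set the variance. The plan lists the zero difference among its usual parameters and brings in the rates when it turns to the variance, so the table can be read as a variance sensitivity table at difference 0. High rates are indeed pessimistic for the variance. This is a plausible account of how the table was built, but it does not rescue it. The text calls the rates true, claims power at them, and nowhere says that power is taken at equal rates. At difference 0 the stated variance and 68 patients give about 37%.

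Four further points carry weight:

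- **Small effect alone.** Correcting the labels moves power at difference 0 by less than 2 points, so the case does not rest on a large numerical effect of the labels.
- **The 5% is conditional.** It applies only if PPA is the tested arm. The analysis plan's only hypothesis statement tests EDA, and in that direction the shortfall is moderate.
- **Some cells match.** The plan describes concordance on a success/failure scale, so readings F and G have textual support. They come within 3 points of every printed cell, and the printed 92% and 86% fall inside the range over all readings. The printed 90% and 83% do not. F and G also imply a column 1 variance of 0.34 to 0.35, against the stated 0.40.
- **The numbers do not prove the route.** The recovered calculation is algebraically the same as a two-sample formula with 68 per arm, standard deviation 0.40 and distance 0.20. That difference 0 was used rests on the plan's text.

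**Conclusion.** The concern holds. The plan assumes a zero difference while presenting its power at rates that differ by exactly the margin, and no reading consistent with its stated variance returns the printed row for 68 patients.

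The firmest result is column 1: 83% with EDA tested or 5% with PPA tested, against 90% printed. For the other columns the size depends on how concordance is read: 85 to 94%, 79 to 82% and 81 to 88% with EDA tested, and 5% with PPA tested. These figures assume a one-sided 5% test, the paired normal approximation, and 68 patients with both outcomes observed. The direction of the test has to be settled before any single power figure can be stated.

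**What to change.** - Reconcile which arm is tested for non-inferiority between the Antibiotic protocol and the Statistical analysis plan, and state whether the 5% is one-sided.
- Define concordance by a formula, saying whether it refers to infection or to success.
- Rebuild the table with equal EDA and PPA rates, in line with the zero difference, and derive each variance from those rates. If unequal rates are kept as a sensitivity case, print the power at the actual 10-point difference in the stated direction.
- Delete or correct the sentence claiming excellent power at 35% and 45%.
- Correct the variance and per-sequence error at the same time, so that the table is rebuilt once.

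The cost is text only: one table, one sentence, one hypothesis statement and one definition. Conduct and data collection do not change. The stated power at the tabulated rates becomes less favourable. Any change in sample size would come from the variance and per-sequence correction, not from this point.
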